### 3.6 Study Timeline

#### 3.6.1 Primary Completion

The study will reach the final procedure for primary outcome 24 months from the time the study opens to accrual.

#### 3.6.2 Study Completion

The study will reach primary completion of data collection 36 months from the time the study opens to accrual.

## 4 Study Drug

### 4.1 Description, Supply and Storage of Selinexor

Tablets for selinexor oral administration will be supplied in two (2) strengths: 10 and 25 mg of active ingredient per tablet. Bulk bottles of 50 tablets per bottle will be supplied for each of the two strengths. The tablets are clear coated with Opadry II clear and prepared from a common blend prepared from a wet granulation of active compound (selinexor), Kollidon® 30 (polyvinyl pyrrolidone), sodium lauryl sulfate, croscarmellose sodium, and Avicel PH-101 (Microcrystalline cellulose). The granulation is adjusted to final compression blend with Avicel PH-102 (Microcrystalline cellulose), Aerosil® (colloidal silicon dioxide), magnesium stearate, and additional croscarmellose sodium. All tablet excipients are GRAS and suitable for use in pharmaceuticals.)

Classification - Cell biological modifier: Apoptosis-inducing agent

Mechanism of Action - Selinexor is a small molecule, potent, oral Selective Inhibitor of Nuclear Export (SINE). Selinexor forms a slowly reversible ( $t_{1/2}$  ~24 hours) covalent bond with XPO1 (also called CRM1) at cysteine 528. Selinexor is a potent inhibitor ( $IC_{50}$  ~20nM) of XPO1-mediated nuclear export in intact cells and to have minimal activity (>10  $\mu$ M)

against 114 other proteins including enzymes, receptors, transporters, ion channels and other CysteinyI-active site kinases and proteases in binding assays.

Metabolism - preliminary analysis from a subset of patients (N=22) suggests that the primary metabolism of selinexor in plasma is through glucuronidation as well as hydroxylation and addition of cysteine/glycine groups (derived from GSH conjugation) to the parent compound. Relative proportions of the putative metabolites are low, typically less than 1% of parent at peak selinexor concentrations and these metabolites are not expected to be pharmacologically active.

Availability - Selinexor will be supplied by Karyopharm Therapeutics Inc.

Storage and handling - Selinexor tablets will be stored at ambient or refrigerated temperatures between (36 – 86 °F) or (2–30 °C) in a locked and secured area with restricted access to study staff. The tablets should not be stored at freezer temperatures or allowed to freeze. Tablets will be supplied in white high density polyethylene (HDPE) bottles.

Side Effects – >200 patients have been treated with selinexor to date. The most common adverse events (AEs) are gastrointestinal in nature: nausea, anorexia, vomiting. Fatigue is also observed, and, like the nausea, is sometimes associated with anorexia. Mucositis or stomatitis are not observed, consistent with nonclinical toxicological studies. Active administration of appetite stimulating agents, leads to markedly improved tolerability. In addition, anorexia appears to decline with longer treatment on selinexor. Idiosyncratic reductions in platelets have been observed; these were not seen in any of the nonclinical models. No cases of clinically significant bleeding have been reported to date. Neutropenia and anemia are minimal, consistent with a lack of myelosuppression observed in nonclinical studies. Ocular symptoms of various kinds (blurred vision is the most common one) have been reported by a number of patients. Other than changes in visual acuity, corrected with new prescriptions in a few cases, no objective findings on ophthalmological examination have been associated with these ocular symptoms, except for five patients that had experience worsening of pre-existing cataracts. No major organ toxicities or drug-related deaths have been observed to date. Patients with advanced cancers have remained on selinexor for >10-12 months. Complete and updated adverse event information is available in the Investigational Drug Brochure.

Based on the experience of >200 patients, each patient in this study will be assessed periodically for the development of any toxicity as outlined in Section 6 of this protocol. Toxicity will be assessed according to the NCI CTCAE v4.0. Dose adjustments will be made according to the system showing the greatest degree of toxicity, as described in Section 5.2.

## 4.2 Drug Accountability

The Investigational Pharmacist will manage drug accountability records.

## 4.3 Drug Ordering

UCSF will obtain selinexor directly from Karyopharm Therapeutics as study supply.

#### 4.4 Packaging and Labeling of Study Drug

Each bottle of selinexor tablets will be labeled in accordance with current ICH GCP, FDA and specific national requirements.

Drugs will be packaged and labeled per UCSF institutional standards, adhering to applicable local and federal laws.

### 5 Treatment Plan

#### 5.1 Dosage and Administration

Treatment will be administered on an outpatient basis. Patients will be provided with a study diary for documentation of selinexor administration. Study diaries will be collected every cycle.

**Table 5.2.1 Regimen Description**

Study Drug	Premedication; precautions	Dose	Route	Schedule	Cycle Length
Selinexor	Pre-medicate with ondansetron 8 mg PO q8h on D0-D3 and olanzapine (2.5-5.0 mg QHS) on D1 and D3*	60 mg	Oral	Ondansetron: four-times weekly (D0 – D3) of each 4-week cycle. Olanzapine: Twice weekly (D1 and D3 of each week 1 – 3 of each 4-week cycle. Drug holiday on week 4).	4 weeks (28 days)

\*Prophylaxis prior to initiation of therapy with selinexor is recommended.

Selinexor will be administered at a starting dose of 60 mg on D1 and D3 of weeks 1 – 3 of each 4 week cycle, with subsequent dose titration for dose limiting toxicity (Table 5.3).

- All adjustments of dose must be maintained either in the pharmacy records or subject’s medical records.

Number of Tablets per Total Mg Dose		
Mg Dose (from Rounded Dose Table)	Number of Tablets of Each Strength	
	10 mg tablets	25 mg tablets
20	2	0
40	4	0
60	1	2

Patients will receive prophylactic treatment to prevent anorexia and nausea, which will include the following:

- Ondansetron 8 mg PO q8h on day prior to and day of dosing (D0-D3)
- Olanzapine 5 mg PO qbedtime or 2.5 mg PO BID on day of dosing (D1, D3)

If nausea and/or anorexia persist despite administration of ondansetron and olanzapine on the days of dosing, additional prophylactic treatment may include the addition of any of the following:

- Dexamethasone 2-4 mg PO BID on days of dosing (D1, D3)  
AND/OR
- Olanzapine 5 mg PO qbedtime or 2.5 mg PO BID on days prior to dosing (D0, D2)  
AND/OR
- Megestrol acetate 160-400 mg daily, 0-3 days before the first dosing day of KPT-330  
AND/OR
- Mirtazapine 15 mg qd (qpm/qhs), 0-3 days before the first dosing day of KPT-330  
AND/OR
- Marinol 5 mg PO BID  
AND/OR
- NK1R antagonist: Aprepitant 120 mg PO x1 on D1, then 80 PO qAM on D2-D3 of each dosing week or equivalent should be considered and will be covered for selected patients who have severe nausea and vomiting.

If the patient is on steroids coming on the study, megestrol acetate should be added prophylactically to prevent anorexia. Other androgenic-anabolic steroids including exogenous testosterone or synthetic testosterone derivatives (e.g., oxandrolone) are contraindicated in patients with metastatic castration resistant prostate cancer, and therefore must not be administered at any point during trial participation.

If an increased risk of adverse effects due to olanzapine is anticipated, olanzapine can be omitted. However, it is recommended that mirtazapine or other appetite stimulating serotonergic agent be used. Additional standard supportive care agents may be used as needed (prn), and as per table 5.3.

Supportive care may be tapered or discontinued in Cycle 2 or later in patients who tolerate selinexor well in Cycle 1.

## 5.2 Dose Modifications and Dosing Delays

If a patient experiences an intolerable toxicity (CTCAE v4.0 Grade 3 or 4) selinexor should be held. Following resolution of the toxicity to Grade 1 or to the patient's baseline value the patient may resume treatment with study drug. In general, patients who resume therapy following toxicity should resume treatment at a lower dose level assessed to be safe. However, following recovery from toxicity that was not considered clinically important, and that could be managed if it were to recur (e.g., replacement of an electrolyte), the patient may resume therapy without dose reduction if the Investigator considers this to be in the best interest of the patient. Provisional dose levels for selinexor are listed in Table 5.2.

Management of severe or intolerable adverse reactions may require dose reduction and/or interruption of the study drug. Recommendation of dose reduction, interruption or discontinuation in the management of adverse reactions are summarized below. Clinical judgment of the treating physician should guide the management plan of each patient based on individual benefit/risk assessments.

If a patient requires a dose delay > 21 days due to a study drug-related toxicity, then the patient must be discontinued from the study unless the patient has experienced evidence of clinical benefit. If the patient has experienced evidence of clinical benefit, and in the opinion of the Investigator it is in the best interest of the patient to remain on treatment, the patient may continue on study after discussion and with approval by Karyopharm.

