This Phase 2 study will begin dosing selinexor at 60 mg flat dose, twice per week at least 48 hours apart (Mon/Wed, Tue/Thurs or Wed/Fri) on Weeks 1, 2 and 3 of a 4-week cycle. Recent analysis of the existing PK data from Phase 1 trials KCP-330-001 and KCP-330-002 supports the use of fixed rather than BSA-based dosing. The 5th and 95th percentile for BSA values encountered to date in Phase 1 trials KCP-330-001 and KCP-330-002 are 1.5 and 2.3 m^2, respectively (N=331). PK values ( $C_{max}$  and  $AUC^{(0-\infty)}$ ) for a given flat (fixed) dose of selinexor were similar across this typical BSA range, indicating that exposure is not strongly correlated with BSA. Selinexor will not be taken during Week 4 (total six doses per cycle). Cycles are repeated every 28 days until disease progression. For each patient, dose reductions of Selinexor is allowed until the dose has been reduced below 20 mg dose per week, at which time treatment will be discontinued.

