**Table 5.2 Dose Modifications and Dosing Delays for patients demonstrating clinical response or stable disease**

Dose level	Dose of selinexor
Dose level 0	60 mg twice weekly (D1, D3 on weeks 1, 2, 3 of each 4 week cycle)
Dose level -1	40 mg twice weekly (D1, D3 on weeks 1, 2, 3 of each 4 week cycle)
Dose level -2	20 mg twice weekly (D1, D3 on weeks 1, 2, 3 of each 4 week cycle)
Dose level -3	20 mg once weekly (D1 on weeks 1, 2, 3 of each 4 week cycle)
Dose level -4	Discontinue dosing

Patients will continue to receive selinexor until they need to have their dose reduced below 20 mg once weekly dose, at which time treatment will be discontinued.

Treatment or visit delays for public holidays or weather conditions do not constitute a protocol violation.

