
Notes: All dose modifications should be based on the worst preceding toxicity.
 
Isolated values of <math>\geq</math> grade 3 alkaline phosphatase values will NOT require dose interruption. Determination of liver vs. bone etiology should be made, and evaluation of GGT, 5'NT, or other liver enzymes should be performed.
 
<math>\geq</math> Grade 3 anemia judged to be a hemolytic process secondary to study drug will require interruption of study treatment until resolved to <math>\leq</math> Grade 1. Selinexor may then be re-instituted at 2 levels below original dose (Table 5.2 ).
 
<math>\geq</math> Grade 3 lymphopenia considered clinically significant will require dose interruption until resolved to <math>\leq</math> grade 2, then reduce by 1 dose level.
 
Patients are allowed dose reductions to a minimum dose of 35 mg/m^2 as described in Table 5.2
 
If a patient requires a dose interruption of >21 days due to a study drug related toxicity, then the patient must be discontinued from the study. Patients who discontinue the study for a study related adverse event or abnormal laboratory value must be followed at least once a week for 28 days and subsequently at 28 day intervals until resolution or stabilization of the event, whichever comes first.
	

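### Two notes under Table 5.3 contradict Section 5.2 and Table 5.2 on the minimum dose and the 21-day delay; schedule and restart wording need smaller repairs

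*Combined protocol and SAP*

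**What the plan says.** All references are to the combined protocol and SAP.

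**Minimum dose.** Table 5.2 is a flat-dose ladder: 60, 40 and 20 mg twice weekly (levels 0, -1, -2), then level -3, "20 mg once weekly (D1 on weeks 1, 2, 3 of each 4 week cycle"). The text below it keeps patients on treatment "until they need to have their dose reduced below 20 mg once weekly dose, at which time treatment will be discontinued". Section 1.4 has the same weekly floor of 20 mg. The notes to Table 5.3 say instead: "Patients are allowed dose reductions to a minimum dose of 35 mg/m" squared, and cite Table 5.2 as the source.

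**21-day delay.** Section 5.2 discontinues a patient whose drug-related delay exceeds 21 days. It makes an exception for clinical benefit, subject to the investigator's opinion and the drug supplier's approval. The notes to Table 5.3 state the rule for an interruption of more than 21 "days due to a study drug related toxicity, then the patient must be discontinued from the study", with no exception.

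**Schedule.** In Table 5.3, the row for bilirubin at 1.5 to 3 times the upper limit of normal (ULN) and the grade 2 diarrhea row step down to once-weekly dosing and then return to twice weekly. The grade 3/4 diarrhea row restarts twice weekly at the reduced level.

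**Restart grade.** After grade 3 or 4 toxicity, Section 5.2 says: "Following resolution of the toxicity to Grade 1 or to the patient's baseline value the patient may resume treatment with study drug". Several Table 5.3 rows use a different threshold.

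**Precedence.** Section 4.1 says: "Dose adjustments will be made according to the system showing the greatest degree of toxicity, as described in Section 5.2". Section 5.1 sends titration to the table: "with subsequent dose titration for dose limiting toxicity (Table 5.3"). No sentence ranks one over the other.

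**The concern.** Dose modification is carried out at several sites by staff reading these tables. A site that applied the 35 mg/m² note could not use any reduction step in Table 5.2. A site that followed the 21-day note would have to take off study a patient whom Section 5.2 lets continue. The first is a safety matter, and the second decides whether a benefiting patient keeps the drug.

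The floor also enters a decision rule. The 18-patient safety check in Section 8.3 counts toxicity that rules out selinexor at every dose level, so the lowest permitted level has to be unambiguous.

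**Working it through.** **1. The 35 mg/m² floor against Table 5.2.** Section 1.4 gives the range of body surface area (BSA): the 5th and 95th "percentile for BSA values encountered to date in Phase 1 trials KCP-330-001 and KCP-330-002 are 1.5 and 2.3 m" squared. I assume that this range applies to patients in this trial.

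- Flat dose equal to the floor = 35 × BSA: 35 × 1.5 = 52.5 mg and 35 × 2.3 = 80.5 mg.
- BSA at which the floor equals the starting dose: 60 / 35 = 1.71 m². Above that, the floor exceeds the dose at which every patient starts.
- Level -1 per m²: 40 / 1.5 = 26.7 down to 40 / 2.3 = 17.4 mg/m².
- Levels -2 and -3 per m²: 20 / 1.5 = 13.3 down to 20 / 2.3 = 8.7 mg/m².

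Every reduced level is below 35 mg/m² across the whole range. The note and the ladder cannot both apply.

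**2. The 21-day rules side by side.** Take a patient with clinical benefit, a drug-related delay of more than 21 days, and the supplier's agreement to continue. Section 5.2 permits continuation; the Table 5.3 note forbids it. Both are general rules covering any drug-related toxicity, so preferring the more specific text does not decide between them. The asymptomatic amylase/lipase row, which stops treatment at 3 weeks, is different. It is a stricter rule for one toxicity and can stand.

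**3. Schedule at the bottom of the ladder.** Weekly dose = dose × doses per week, in dosing weeks:

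| Level | Calculation | mg per week |
|---|---|---|
| 0 | 2 × 60 | 120 |
| -1 | 2 × 40 | 80 |
| -2 | 2 × 20 | 40 |
| -3 | 1 × 20 | 20 |

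- Grade 3/4 diarrhea at level -2: the reduced level is -3, at 20 mg a week. Taking the row's twice-weekly schedule literally gives 2 × 20 = 40 mg a week, which is no reduction.
- Bilirubin 1.5 to 3 × ULN, or grade 2 diarrhea, at level -3: the patient is already on once-weekly dosing, so the step down changes nothing. A literal return to twice weekly would be 40 mg a week, which is level -2.

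**4. Restart thresholds, Section 5.2 (grade 1 or baseline) against Table 5.3.**

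- Grade 2 or lower: fatigue, anorexia, nausea, AST/ALT, diarrhea, asymptomatic amylase/lipase and the lymphopenia note. Bilirubin also resumes at grade 2 or lower, but then follows the once-weekly guidance.
- Neutropenia: grade 4 restarts above 800/mm³, still inside the table's grade 3 band of 500 to 1,000. Grade 3 is not held.
- Grade 1 or lower, close to Section 5.2: hyponatremia, thrombocytopenia, other cardiac events, grade 3 neurotoxicity and the grade 3 line of the row for other events.
- Stricter than Section 5.2: the grade 4 line of that last row discontinues selinexor unless another cause is found.

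**The case against.** The best defense is that most of this resolves on a sensible reading. Section 5.2 is permissive, introduces the detailed recommendations that follow it, and defers to the treating physician's judgment. Different restart grades for different toxicities are ordinary design. The 35 mg/m² note names Table 5.2 as its source, and the tablet table in Section 5.1 also lists only 20, 40 and 60 mg, so the note looks like leftover text. The supplier's approval limits how far sites can diverge after day 21. The schedule mismatch needs two or three earlier reductions, and the diarrhea rows apply only when maximal anti-diarrheal treatment has failed.

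Much of that stands. A reader might infer that Section 5.2 and Table 5.3 are rival systems under which sites would restart the same patient at different grades. The documents do not support so strong a reading: the table's specific rows naturally govern, and only the statement to that effect is missing. A reader might also infer that a level -3 patient is told to double the dose. That is literal but implausible, because a restart suggests the previous schedule and the text under Table 5.2 sets a floor.

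The defense does not remove the first two points. The 35 mg/m² note sits among the operative notes and is wrong as written. The 21-day texts are both general, and clinical judgment cannot override an unconditional requirement to discontinue.

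**Conclusion.** The point holds, mainly for two rules.

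- **Minimum dose:** the Table 5.3 note equals 52.5 to 80.5 mg per dose, against a ladder that descends to 20 mg once weekly. This rests on the Section 1.4 BSA range.
- **21-day delay:** Section 5.2 allows continuation under conditions, and the Table 5.3 note does not.

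The schedule wording is minor: 40 rather than 20 mg a week for grade 3/4 diarrhea at level -2, and an unclear instruction at level -3. Such cases should be few, since Table 5.3 labels bilirubin toxicity rare and diarrhea uncommon. The restart-grade difference is also minor and is a missing statement of precedence.

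A reader might infer that these conflicts bias radiographic progression-free survival or alter the design's error rates. The documents do not show this. They give no frequency for delays beyond 21 days or for reductions to the lowest levels, so the number of patients affected cannot be estimated.

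**What to change.** 1. Replace the 35 mg/m² note under Table 5.3 with the Table 5.2 floor of 20 mg once weekly.
2. Carry the Section 5.2 exception (clinical benefit, investigator opinion, supplier approval) into the 21-day note under Table 5.3, so that both places give one rule. Keep the 3-week amylase/lipase stop as a stricter row-specific rule.
3. In the diarrhea and bilirubin rows, replace the twice-weekly wording with the schedule of the assigned Table 5.2 dose level. State that a patient at level -3 who needs a further reduction discontinues, as the text under Table 5.2 already provides.
4. Optionally, add to Section 5.2 that all Table 5.3 rows, including the row for other events with its grade 4 discontinuation, and the notes on alkaline phosphatase, hemolytic anemia and lymphopenia, govern where they differ from the general restart rule.

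Three shortcuts should be avoided. Sending every toxicity without its own row to the grade 1 or baseline rule would displace the grade 4 discontinuation and the note that isolated alkaline phosphatase elevation needs no interruption. Declaring that Table 5.3 governs without correcting its floor would import the 35 mg/m² minimum. Requiring a hold at level -3 would be a new clinical rule.

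The cost is a protocol wording amendment. It adds no assessments and changes no Table 5.3 restart threshold.

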**Table 5.2 Dose Modifications and Dosing Delays for patients demonstrating clinical response or stable disease**

Dose level	Dose of selinexor
Dose level 0	60 mg twice weekly (D1, D3 on weeks 1, 2, 3 of each 4 week cycle)
Dose level -1	40 mg twice weekly (D1, D3 on weeks 1, 2, 3 of each 4 week cycle)
Dose level -2	20 mg twice weekly (D1, D3 on weeks 1, 2, 3 of each 4 week cycle)
Dose level -3	20 mg once weekly (D1 on weeks 1, 2, 3 of each 4 week cycle)
Dose level -4	Discontinue dosing

Patients will continue to receive selinexor until they need to have their dose reduced below 20 mg once weekly dose, at which time treatment will be discontinued.

Treatment or visit delays for public holidays or weather conditions do not constitute a protocol violation.

### 5.3 Monitoring and Toxicity Management

Each patient receiving selinexor will be evaluable for safety. The safety parameters include all laboratory tests and hematological abnormalities, physical findings, and spontaneous reports of adverse events reported to the investigator by patients.

Each patient will be assessed periodically for the development of any toxicity as outlined in [Section 6 Study Procedures and Observations](#). Toxicity will be assessed according to the NCI [CTCAE v4.0](#). Dose adjustments will be made according to the system showing the greatest degree of toxicity.

We will monitor for anorexia, loss of appetite, fatigue, thrombocytopenia, neutrocytopenia, diarrhea, blurred vision, liver enzyme increase, and hyponatremia.

Acute toxicity will be managed by supportive care or delay of dose. Further management will depend upon the judgment of the clinician, and may include dose reduction.

Treatment will be started at a dose of 60 mg administered twice weekly. For those patients experiencing dose limiting toxicity (as defined below) yet thought to be benefiting from therapy (i.e., reduction in PSA, reduced pain, or reduction in size and/or number of bony metastases), the treatment dose will be reduced per Table 5.2. Subsequent reductions for persistent grade 3 toxicities will include dose reduction per Table 5.2.

**Table 5.3 Criteria for dose adjustments of Selinexor-related toxicities**

Toxicity and Intensity	Dose Modification
Fatigue (common)	
Grade 1	Insure adequate caloric intake and assess volume status. Adjust other medications. Consider addition/increased dose of corticosteroids (e.g., 2-4 mg BID dexamethasone the day of selinexor dosing). Rule out other causes of fatigue such as adrenal insufficiency or thyroid dysfunction.
Grade 2	Insure adequate caloric and fluid intake and assess volume status. May consider additional corticosteroid, per clinician discretion. If fatigue dose not resolve to Grade 1, reduce dose of selinexor by one level (Table 5.2).
Grade 3	Insure adequate caloric and fluid intake and assess volume status. Interrupt selinexor dosing until resolved to Grade $\leq$ 2, reduce dose of selinexor by 1 level (Table 5.2).
Anorexia (common)	
Grade 1	Assess dietary options (e.g. try a variety of other foods). Add high-calorie supplements (e.g., Ensure®). If fatigue or nausea also present, consider addition/increased dose of dexamethasone (e.g., 2-4 mg dexamethasone BID on the day of selinexor dosing), or consider addition of other anti-emetic per section 5.1

Toxicity and Intensity	Dose Modification
Grade 2	Add high-calorie supplements (e.g., Ensure®). Consider addition/increased dose of dexamethasone (e.g., 2-4mg dexamethasone BID on the day of selinexor dosing and/or on the day prior to dosing, or consider addition of other anti-emetic per section 5.1. Consider dronabinol (Marinol®). Skip intermittent doses of selinexor while supportive medications are instituted. If Grade 2 anorexia does not resolve after institution of supportive medications, reduce selinexor dose by 1 level (Table 5.2).
Grade 3	Interrupt dosing with selinexor. Add high calorie supplements. Use supportive medications alone or in combinations. Restart selinexor at 1 dose level reduction (Table 3) once anorexia resolves to Grade ≤2. If Grade 2 anorexia persists with supportive medications, reduce dose of selinexor another level (Table 5.2).
Nausea/Emesis (common)	
Grade 1	D2 antagonists, addition/increased dose of corticosteroids (e.g., 2-4mg dexamethasone with each dose of selinexor the day prior to dosing), NK1 antagonists, or dronabinol (Marinol) or combinations can prevent nausea in the majority of patients.
Grade 2	Implement one or more combinations of additional anti-nausea medications per section 5.1. If nausea does not resolve to Grade ≤1, reduce dose of selinexor by one dose level (Table 5.2).
Grade 3	Implement one or more combinations of anti-nausea medications per section 5.1 and interrupt dosing of selinexor. Selinexor may be restarted with one dose level reduction (Table 5.2) when nausea is Grade ≤2 and adequate caloric and fluid intake have been achieved.
Hematologic	
Neutropenia (rare)	
Grade 1 (ANC < LLN - 1500/mm  ) Grade 2 (ANC < 1500 - 1000/mm  ) Grade 3 (ANC < 1000 - 500/mm  )	Maintain dose level  The use of growth factors during selinexor treatment is permitted and in patients with poor marrow function, encouraged. If ANC drops to <1000/mm  , growth factors are encouraged to reduce dose interruptions.
Grade 4 (ANC < 500/mm  )	Delay study treatment until ANC returns to >800/mm  , then: If increased to >800/mm  by ≤ 7 days after suspending selinexor, maintain dose level If increased to >800/mm  by > 7 days after suspending selinexor, then reduce by 1 dose level (Table 5.2). The use of growth factors during selinexor treatment is encouraged.

Toxicity and Intensity	Dose Modification
Febrile neutropenia, or fever of unknown origin without clinically or microbiologically documented infection (ANC $<1.0 \times 10^9/L$ , fever $\geq 38.5^\circ C$ )	Delay study treatment until patient has stabilized, then reduce selinexor by 1 dose level (Table 5.2). Selinexor may be re-initiated at the reduce dose when patient's condition has stabilized following initiation of antibiotic therapy. Selinexor dose may be re-escalated up one level (Table 5.2) after $\geq 1$ cycle at the reduced dose provided ANC is adequate.
Thrombocytopenia (Platelets) (uncommon)	
Grade 1 (PLT $< LLN - 75,000/mm^3$ )	Maintain dose level.
Grade 2 (PLT $< 75,000 - 50,000/mm^3$ )	Delay selinexor treatment until resolved to $\leq$ grade 1
Grade $\geq 3$ (PLT $< 50,000 - 25,000/mm^3$ ) without bleeding	Delay selinexor treatment until resolved to $\leq$ grade 1 and restart at one dose level below (Table 5.2 ). All patients with Grade 4 thrombocytopenia should have a manual blood smear analysis to determine if clumping (e.g., "pseudo-thrombocytopenia") and/or giant platelets are present. Platelet transfusions may be given to support platelet levels in patients with clear clinical benefit from selinexor.
Grade 4 (PLT $< 25,000/mm^3$ ) without bleeding	Delay study treatment until resolved to $\leq$ grade 3, then follow guidelines above.
Platelet Stimulators	The use of platelet stimulators may be considered in patients with a history of thrombocytopenia or compromised marrow function, or in patients in whom selinexor is having demonstrable clinical benefit. IL-11 (oprelvekin, Neumega®), eltrombopag (Promacta®), or romiplostim (N-Plate®) should be considered.
Hyponatremia (common)	
Grade 1 (Lower Limit of Normal to 130nM)	Maintain dose level, assure adequate fluid, electrolyte and caloric intake, adjust other medications, consider salt supplementation, rule out other causes.
Grade 3 (120-130nM)	Discontinue selinexor until resolved to grade $\leq 1$ then reduce dose by 1 level. Check renal function, serum and urinary electrolytes, and rule out other causes.
Renal (rare)	
Serum creatinine	
Calculated or measured creatinine clearance $\geq 20$ cc/min	Maintain dose level
Calculated or measured creatinine clearance $< 20$ cc/min	Reduce selinexor by 1 dose level until resolved. Dose may also be re-escalated if lower dose is tolerated after 1 full cycle.
Hepatic (rare)	
Bilirubin	
Total bilirubin $< 1.5 \times ULN$	Maintain dose level

Toxicity and Intensity	Dose Modification
Total bilirubin 1.5 - 3 x ULN	Reduce selinexor to once weekly dosing until resolved to ≤ Grade 1, then restart twice weekly dosing
Grade 3 (> 3.0 - 10.0 x ULN) Grade 4 (> 10.0 x ULN)	Discontinue selinexor until resolved to Grade ≤2, then follow guidelines above. Note: If Grade 3 or Grade 4 hyperbilirubinemia is due to the indirect component only, and hemolysis as the etiology has been ruled out as per institutional guidelines (e.g. review of peripheral blood smear and haptoglobin determination), then reduce selinexor dose by 1 level (Table 5.2) and continue treatment at the discretion of the investigator. Discontinuation of selinexor is required if concurrent elevations of total bilirubin > 2.0 X upper limit of normal (ULN) and ALT or AST > 3.0 X ULN are observed and other causes have been ruled out. In order to characterize hepatic toxicity more precisely, fractionation of bilirubin and alkaline phosphatases will be required for elevated values > 2.0 X ULN and ≥ CTCAE Grade 2, respectively.
AST or ALT (rare)	
Grade 1 (> ULN - 2.5 x ULN)	Maintain dose level
Grade 2 (> 2.5 - 5.0 x ULN)	Delay selinexor until resolved to Grade ≤1, then maintain dose level. Consider addition of S-adenosylmethionine (SAM) 400mg qd-bid.
Grade 3 (> 5.0 - 20.0 x ULN)	Delay selinexor until resolved to ≤ grade 2, then reduce by 1 dose level (Table 5.2 ). Consider addition of S-adenosylmethionine (SAM) 400mg qd-qid. If no further AST or ALT elevations occur during one cycle (4 weeks) at the reduced dose level, then dose may be continued at the reduced dose. Discontinuation of selinexor is required if concurrent elevations of direct bilirubin > 2.0 X upper limit of normal (ULN) and ALT or AST > 3.0 X ULN are observed. In order to characterize hepatic toxicity more precisely, fractionation of bilirubin and alkaline phosphatases will be required for elevated values > 2.0 X ULN and ≥CTCAE grade 2, respectively.
Grade 4 (> 20.0 x ULN)	Delay selinexor until resolved to ≤ Grade 2, then reduce by 2 dose levels
Cardiac (rare)	
Hypertension	Treatment-emergent hypertension should be treated as per standard cardiology practice. Recommended agents for the management of blood pressure elevations on selinexor include angiotensin-converting enzyme inhibitors and calcium channel blockers.
Grade 1	Maintain dose level

Toxicity and Intensity	Dose Modification
Grade 2 / 3	Delay selinexor and initiate/intensify antihypertensive therapy. Selinexor may be restarted in conjunction with standard anti-hypertensive medication if BP is controlled (i.e BP $\leq$ 150/100 mmHg). If BP is controlled $\leq$ 7 days after suspending selinexor, maintain dose level If BP is controlled $>$ 7 days after suspending selinexor, then reduce by 1 dose level
Grade 4	Delay the selinexor and initiate/intensify antihypertensive therapy, then reduce by 1 dose level. Selinexor may be restarted in conjunction with anti-hypertensive medication if BP is controlled (i.e BP $\leq$ 150/100 mmHg).
Cardiac – Other (rare)	
Grade 1 or 2	Maintain dose level
Grade 3	Delay selinexor until resolved to $\leq$ Grade 1, then reduce by 1 dose level (Table 5.2).
Grade 4	Discontinue study treatment
Diarrhea (uncommon)	
Grade 1 (despite maximal anti-diarrheal medication)	At the first sign of abdominal cramping, loose stools, or onset of diarrhea, it is recommended that the patient be treated according to institutional standard of care. Maintain dose level of selinexor.
Grade 2 (despite maximal anti-diarrheal medication)	Reduce to selinexor to one weekly until resolved to $\leq$ grade 1, then re-start twice weekly at the current dose level. If diarrhea returns as $\geq$ Grade 2, then reduce selinexor dose by one dose level and dose once weekly until resolved to $\leq$ grade 1, then re-start twice weekly at reduced dose level
Grade 3/4 (despite maximal anti-diarrheal medication)	Delay selinexor until resolved to $\leq$ grade 2, then re-start twice weekly at reduced dose level
Neurotoxicity (not observed to date)	
CTCAE grade 1 / 2	Grade 0 $\rightarrow$ Grade 1: maintain dose level Grade 0 or 1 $\rightarrow$ Grade 2 : delay study treatment until resolved to $\leq$ Grade 1, then reduce by 1 dose level (Table 5.2).
CTCAE grade 3	Discontinue study treatment until resolved to Grade $\leq$ 1 then reduce by 2 dose levels (Table 5.2 ).
CTCAE grade 4	Discontinue study treatment.
Amylase and/or lipase elevations (rare)	
Grade 1 or 2	Maintain dose level
Asymptomatic Grade 3 or 4	Delay selinexor until $\leq$ Grade 2, then restart at 1 dose level reduction (Table 3). Rule out other causes of amylase/lipase elevation. If levels have not returned to $\leq$ Grade 2 within 3 weeks then no further selinexor may be given and the patient should discontinue permanently from the study. A CT scan or other imaging study to assess the pancreas, liver and gallbladder must be performed within 1 week of the first occurrence of any grade 3 elevation of amylase and/or lipase.

Toxicity and Intensity	Dose Modification
Symptomatic Grade 3 or 4	Selinexor must be stopped immediately and proper supportive care provided. Evaluate enzyme levels at least twice weekly until resolution to $\leq$ Grade 1. Clinical manifestations should be monitored as needed until resolution or stabilization of the disease condition. Selinexor may be re-started at 2 dose levels below (Table 5.2) after resolution to $\leq$ Grade 1.
Pancreatitis (not observed to date)	
Grade 1	Maintain dose level
Grade 2, 3 or 4	Discontinue study treatment.
Other Selinexor-related adverse events	
Grade 1 or 2	Maintain dose level and initiate standard supportive care.
Grade 3	Delay dose until resolved to $\leq$ Grade 1, then reduce by 1 dose level
Grade 4	Discontinue selinexor and rule out other causes. If other causes of Grade 4 adverse event are uncovered, selinexor may be re-initiated at 1 dose level reduction (Table 5.2).

Notes: All dose modifications should be based on the worst preceding toxicity.
 
Isolated values of <math>\geq</math> grade 3 alkaline phosphatase values will NOT require dose interruption. Determination of liver vs. bone etiology should be made, and evaluation of GGT, 5'NT, or other liver enzymes should be performed.
 
<math>\geq</math> Grade 3 anemia judged to be a hemolytic process secondary to study drug will require interruption of study treatment until resolved to <math>\leq</math> Grade 1. Selinexor may then be re-instituted at 2 levels below original dose (Table 5.2 ).
 
<math>\geq</math> Grade 3 lymphopenia considered clinically significant will require dose interruption until resolved to <math>\leq</math> grade 2, then reduce by 1 dose level.
 
Patients are allowed dose reductions to a minimum dose of 35 mg/m^2 as described in Table 5.2
 
If a patient requires a dose interruption of >21 days due to a study drug related toxicity, then the patient must be discontinued from the study. Patients who discontinue the study for a study related adverse event or abnormal laboratory value must be followed at least once a week for 28 days and subsequently at 28 day intervals until resolution or stabilization of the event, whichever comes first.
	

